2.3 Secondary Efficacy Endpoint

2.31 The secondary efficacy endpoint of this study will be VTE recurrence including DVT, PE, fatal PE, or arterial thromboembolism. The following criteria will be used to confirm and categorize a VTE recurrence:

- Suspected (recurrent) DVT: The original DVT must be confirmed by duplex ultrasonography, venography, CT, or MRI. A recurrent DVT must be distinguished from the original thrombus by comparing serial imaging modalities. In order to be classified as a recurrent event, there must be new filling defects evident on the second study not appreciated on the original images or an interval study clearly showing thrombus resolution.
- Suspected (recurrent) PE: The original PE must be confirmed by CT, MR, conventional pulmonary angiography, or VQ perfusion imaging. A recurrent PE must be distinguished from the original thrombus by comparing serial imaging modalities. In order to be classified as a recurrent event, there must be new filling defects evident on the second study not appreciated on the original images or an interval study clearly showing thrombus resolution.

- Fatal PE: PE based on objective diagnostic testing, autopsy, or death which cannot be attributed to a documented cause and for which PE/DVT cannot be ruled out (unexplained death).
- Incidental VTE recurrence: Due to the nature of cancer surveillance related imaging, it is anticipated that recurrent venous thrombosis or thrombus propagation may be identified. In order to be classified as an event, the thrombus in question must be distinguished from the original thrombus by comparing serial imaging modalities. In order to be classified as a recurrent event, there must be new filling defects evident on the second study not appreciated on the original images or an interval study clearly showing thrombus resolution.
- Arterial thromboembolism: Myocardial infarction (MI), stroke, transient ischemic attack (TIA), or peripheral arterial embolism.

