3.0 Patient Eligibility

3.1 Inclusion Criteria

3.11 Age \geq 18 years.

3.12 Confirmed acute index (original venous thrombotic) event: lower extremity or upper extremity (jugular, innominate, subclavian, axillary, brachial) DVT, PE, splanchnic (hepatic, portal, splenic, mesenteric, renal, gonadal), or cerebral vein thrombosis for which the patient has received \geq 180 days (but \leq 365 days) of anticoagulant therapy prior to registration. The date, imaging modality, and location of index event will be required. The date of initiation and specific type of anticoagulants used will also be required.

3.13 Active cancer defined as metastatic disease and/or any evidence of cancer on cross-sectional or PET imaging, cancer related surgery, chemotherapy or radiation therapy within the past 6 months. Note: non-melanoma skin cancer does not meet the cancer requirement.

3.14 Life expectancy \geq 6 months.

3.15 ECOG Performance Status (PS) of 0, 1, or 2. (Form is available on the ACCRU web site
[REDACTED]

3.16 The following laboratory values obtained \leq 30 days prior to registration.

- Hemoglobin \geq 8 g/dL
- Platelet count \geq 50,000/mm³
- Alanine aminotransferase (ALT) or Aspartate transaminase (AST) \leq 3 x ULN
- Calculated creatinine clearance must be \geq 30 ml/min using the Cockcroft-Gault formula below:

Cockcroft-Gault Equation:

$$\text{Creatinine clearance for males} = \frac{(140 - \text{age})(\text{weight in kg})}{(72)(\text{serum creatinine in mg/dL})}$$

$$\text{Creatinine clearance for females} = \frac{(140 - \text{age})(\text{weight in kg})}{(72)(\text{serum creatinine in mg/dL})} * (0.85)$$

3.17 Negative serum or urine pregnancy test done \leq 7 days prior to registration, for women of childbearing potential only.
 Note: A woman of childbearing potential (WOCBP) is defined as any female who has experienced menarche and who has not undergone surgical sterilization (hysterectomy or bilateral oophorectomy) and is not postmenopausal. Menopause is defined as 12 months of amenorrhea in a woman over age 45 years in the absence of other biological or physiological causes.

3.18 Ability to provide informed written consent.

3.19 Willing to undergo monthly follow-up assessment, either in person at the enrolling institution or by telephone (script in Appendix V).

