7.0 Protocol Treatment

7.1 Treatment Schedule

| Agent | Dose Level | Frequency | Route |
|----------|------------|--------------------------------------|-------|
| Apixaban | 2.5 mg | Twice daily for 12 months (365 days) | Oral |
| Apixaban | 5 mg | Twice for daily 12 months (365 days) | Oral |

*If a dose of apixaban is not taken at the scheduled time, the dose should be taken as soon as possible (+/-4 hours of the normal scheduled dose) on the same day and the prescribed dosing schedule should be resumed. If more than 4 hours late, then just wait for the next dose. The dose should not be doubled to make up for missed doses.

7.11 Scheduled visits every 30 days +/- 1 week (either in person or by scripted telephone interview with a study coordinator) should include a standardized assessment for recurrent thromboembolism, bleeding episodes, and adverse reactions. Patients should be instructed to report to the clinic immediately (or call 911/go to the Emergency Room) if they had any bleeding, or symptoms of recurrent deep-vein thrombosis, pulmonary embolism, or both. Written patient education materials will be provided to each patient outlining signs and symptoms to watch for regarding VTE recurrences (appendix VI). All suspected episodes of recurrent thrombosis should be investigated with the use of objective imaging.

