Appendix V
Phone Contact Sheet
Telephone Script

Protocol Title: A Phase III, Controlled, Randomized, Double-Blind Study Evaluating the Safety of Two Doses of Apixaban for Secondary Prevention of Cancer Related Venous Thrombosis in Subjects Who Have Completed at Least Six Months of Anticoagulation Therapy

IRB #:

Principal Investigator: [name]

“Good morning/afternoon. This is _____ calling from [name of institution].

May I speak to _____?”

(If participant is there proceed to the following:)

“I would like to ask you a few questions regarding your blood thinner medication, **apixaban** and the clinical trial in which you have been enrolled. This will allow us to gather very important information about the safety and benefit of using this medication in treating and preventing blood clots.”

“I would like to ask these questions related to our study after confirming your name”

Patient Name _____

1. Over the past month, have you missed any doses of your blood thinner medication?

____ Yes

If yes, approximately how many doses do you estimate that you have missed? _____

If yes, why was the dose missed? _____

____ No, I have not missed any doses of medication

2. Over the past month have you had another blood clot problem?

____ Yes, a DVT (must contact local medical doctor to obtain documentation)

____ Yes, a PE

____ Yes, both a DVT and a PE

____ Yes, something else (e.g. an arterial clot). Please describe: _____

____ No, I have not had any more clots.

3. While you have been taking this medication as recommended have you experienced any major bleeding which required hospitalization or blood transfusion?

____ Yes. Please describe _____

____ No

Any bleeding other than that from an injury? (For example a spontaneous bloody nose.)

____ Yes, Please describe _____

____ No

4. Over the past month, have you undergone any surgeries or invasive procedures?

Yes

If yes, what type of surgery/procedure did you have? _____

What was the date of the procedure? ____-____-____ (MM-DD-YY)

No, I have not had any surgeries or procedures

5. Which of the following best applies to your current activity rating: _____

- A. Fully active, able to carry on all activities before your disease without restriction
- B. Restricted in physically strenuous activity but ambulatory and able to carry out work of a light or sedentary nature, e.g., light house work, office work

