- C. Ambulatory and capable of all self-care but unable to carry out any work activities. Up and about more than 50% of waking hours
- D. Capable of only limited self-care, confined to bed or chair more than 50% of waking hours
- E. Completely disabled. Cannot carry on any self-care. Totally confined to bed or chair

6. What is your current weight? _____

7. Have you started any new medications? List these _____

8. Have you had any new leg swelling?

Yes

i. If yes, suggest that the patient see their medical provider

No, I have not had any new leg swelling.

9. Have you had any new chest pain or shortness of breath?

Yes

i. If yes, instruct the patient to call 911/go to ER.

No, I have not had any new chest pain or shortness of breath.

Do you have any questions for me?

“Thank you for participating in our study.

NOTE: If there is any evidence of bleeding or clotting, review this with the attending clinician and obtain documentation from the local healthcare provider if patient gave consent.

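### Beyond one general question about known clots, the Appendix V telephone script has no symptom prompt for arm/neck, splanchnic or cerebral vein thrombosis, or for stroke, TIA or limb embolism

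*Combined protocol and SAP*

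**What the plan says.** Section 7.11 has visits every 30 days, in person or by scripted telephone interview, and says that each "should include a standardized assessment for recurrent thromboembolism, bleeding episodes, and adverse reactions". Section 3.19 and footnote 3 of the test schedule (4.0) also allow the monthly reassessment to be done by telephone, using Appendix V.

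Three of the script's questions concern thrombosis:

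- Question 2: "Over the past month have you had another blood clot problem". The answers offered are DVT, PE, both, no, and "Yes, something else (e.g. an arterial clot). Please describe".
- Question 8: "Have you had any new leg swelling".
- Question 9: "Have you had any new chest pain or shortness of breath".

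The closing note adds: "If there is any evidence of bleeding or clotting, review this with the attending clinician and obtain documentation from the local healthcare provider", subject to the patient's consent.

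Eligibility under 3.12 covers "lower extremity or upper extremity (jugular, innominate, subclavian, axillary, brachial) DVT, PE, splanchnic (hepatic, portal, splenic, mesenteric, renal, gonadal), or cerebral vein thrombosis". Section 2.31 defines the secondary efficacy endpoint as recurrent VTE or arterial thromboembolism, and lists the arterial events as "Myocardial infarction (MI), stroke, transient ischemic attack (TIA), or peripheral arterial embolism".

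**The concern.** For a patient followed by telephone, the script is the standardized recurrence assessment that 7.11 calls for. Question 2 works at the level of a diagnosis: it finds clots the patient already knows about. Questions 8 and 9 work at the level of symptoms and can find an event nobody has yet diagnosed, but they cover only the leg and the chest. A patient with new arm swelling, new abdominal pain or a brief loss of speech can truthfully answer no to all three.

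Recurrent thrombosis is the harm that would be weighed against any bleeding advantage of the lower dose. If events at some sites are found late or not at all, recurrence is under-counted, and a suspected event does not get the objective imaging that 7.11 asks for.

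**Working it through.** The plan gives no figure on this point, so the check compares the events the plan admits or counts with what the script asks.

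| Event | Where the plan admits or counts it | Symptom prompt in the script | Question 2 |
|---|---|---|---|
| Leg DVT | 3.12, 2.31 | Question 8 | If known to the patient |
| PE | 3.12, 2.31 | Question 9 | If known |
| Myocardial infarction | 2.31 | Question 9, incidentally | If known and seen as a clot |
| Arm or neck DVT | 3.12; 2.31 does not limit DVT to the leg | None | If known |
| Splanchnic vein thrombosis | 3.12; not named in 2.31 | None | If known |
| Cerebral vein thrombosis | 3.12; not named in 2.31 | None | If known |
| Stroke, TIA | 2.31 | None | If known and seen as a clot |
| Peripheral arterial embolism | 2.31 | None | If known |

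**Rest of the script.** The other questions concern missed doses, bleeding, procedures, activity level, weight and new medications. Procedures, activity or new medications might give an indirect clue. No item asks openly about new symptoms, and hospital admission is asked about only in connection with bleeding. The closing note acts on evidence that has already surfaced, so it does not help with a symptom nobody asked about.

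**Other routes of capture.**

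- The test schedule has adverse event assessment every 30 days. Footnote 3 attaches to that row too, so for telephone patients it is obtained through the same interview.
- Section 18.1 requires monthly forms for recurrent thromboembolism and for solicited and other adverse events. The thromboembolism form records what has been learned. The list of solicited events is not shown, so I cannot say whether it includes neurological or limb symptoms.
- Sections 10.4 and 10.52 require reports of serious events, including hospital stays of at least 24 hours, and of Grade 3 and 4 events whatever their cause. A stroke that led to admission should come in this way once the site hears of it. A brief TIA managed at home might not.
- Section 2.31 expects cancer surveillance imaging to reveal some recurrences and counts them. The protocol's own schedule contains no imaging.
- Section 7.11 tells patients to report bleeding and symptoms of DVT or PE at once. It does not mention arterial symptoms. Appendix VI carries a title on DVT and PE, but its content is not visible.

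**Size.** Let m be the fraction of events missed, the same in both arms. The observed rates are then (1 − m)p₁ and (1 − m)p₂. Their difference is (1 − m)(p₁ − p₂), which is smaller than the true one, and their ratio p₁/p₂ is unchanged. Here m is the product of three shares: patients followed by telephone, events at unprompted sites, and such events not caught by any other route. The documents give none of the three, and they give no assumed recurrence rate for either dose in this population.

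**The case against.** The strongest reply is that the script does ask. Question 2 goes to every telephone patient, its DVT option is not confined to the leg, and it names an arterial clot. A reader might infer from questions 8 and 9 that the other sites are never prompted for. The documents do not support that: known clots at any site are prompted for, and only the symptom-level prompt is missing. This part of the reply stands in full.

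It can also be said that serious event reports, the monthly forms and surveillance imaging would catch many of these events. That stands in part. They are real routes, but for telephone patients the adverse event history runs through the same interview, and the others depend on an admission or a scan.

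A reader might further infer a measurable loss of power on the efficacy comparison. That is not supported, for three reasons:

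- The rates and shares needed for a figure are not in the documents.
- Section 16.23 describes its analysis as one of the DVT/PE composite, so missed strokes, TIAs or limb emboli cannot dilute that test as written, although 2.31 counts them.
- Section 2.31 does not name splanchnic or cerebral vein recurrence, so those count only if its general wording on VTE recurrence is read to include them.

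Nor is there a clear reason to expect bias between arms, since both are blinded and use the same script.

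What survives is narrow. By including questions 8 and 9, the script itself does not rely on question 2 alone for leg DVT and PE. It offers nothing equivalent for the other sites it enrols or the other events it counts.

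**Conclusion.** The point holds as a minor gap in ascertainment. On telephone follow-up, thrombosis at arm/neck, splanchnic or cerebral sites, and stroke, TIA or limb embolism, is prompted for only as a clot the patient already knows about. Undiagnosed events may be reported late or missed unless another route catches them.

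The likely effect is under-capture and late work-up on the secondary efficacy endpoint, similar in both arms. The primary bleeding endpoint is unaffected. No numerical size can be supported. The conclusion assumes that some patients are followed by telephone, that interviewers keep to the script, and that neither the solicited adverse event form nor Appendix VI, whose contents cannot be seen, already supplies the missing prompts.

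**What to change.** In Appendix V, beside questions 8 and 9, add yes/no prompts for:

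- new swelling of the arm, neck or face;
- new abdominal pain or swelling;
- new severe headache, visual change, weakness, numbness or difficulty speaking, including episodes that have passed;
- a limb that has become cold, painful or discoloured.

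Extend the closing note so that a yes to any of these goes to the existing attending-clinician review, with suspected thrombosis handled under 7.11 as it stands. Confirmed events go on the Recurrent Thromboembolism form. No dose, eligibility criterion or treatment rule changes.

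The cost is a short amendment to the script, about a minute more per call, and some additional work-ups that turn out negative.

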Appendix VI
Patient Education Material

Deep Vein Thrombosis and Pulmonary Embolism
(©2016 Mayo Foundation for Medical Education and Research)
See next page

Appendix VII

Patient Compliance Information

1. Over the past month, have you missed any doses of your blood thinner medication?

Yes,

If yes, approximately how many doses do you estimate that you have missed?

If yes, why was the dose missed?

No, I have not missed any doses of medication
